### **7.7.5 Severe Angiographic Complications**

The subject-level rate of Severe Angiographic Complications will be assessed post-procedure and presented on the mITT and FAS from CEC adjudicated presence of severe dissections (D-F), perforation, or distal emboli requiring additional treatment during the procedure.

### **7.7.6 Acute Procedure Success**

Acute Procedure Success will be assessed 72 hours after the index procedure and presented on the mITT and FAS. Acute Procedure Success is defined as Acute Technical Success and absence of: death by any cause, stroke, MI, acute onset of limb ischemia, index bypass graft or segment thrombosis, and/or need for urgent/emergent vascular surgery within 72 hours of the clinical trial treatment as adjudicated by the CEC.

### **7.7.7 Major Adverse Event (MAE) Rate**

The MAE Rate will be assessed on a subject level for the mITT and FAS at the time-points of 30 days and 6 months as a time-to-event analysis. The 6-month rates will be evaluated at 210 days (180 days + 30-day visit window). The MAE rate is a composite endpoint comprised of CEC adjudicated:

- death through 30-days (note: subjects with a death after 30-days will be considered censored on the date of death) or,
- major amputation of the target limb (note: major amputation is defined per the protocol as any amputation at or above the ankle joint) or,
- clinically driven TLR (defined as a clinically driven repeat procedure performed for  $\geq 50\%$  stenosis confirmed by angiography within all or part of the target lesion following index procedure)

A subject is considered to have an MAE if any of the above criteria are met. The component rates of MAE may be presented.

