$\geq 180^\circ$ to 269° of calcification	
 
$\geq \frac{1}{2}$ of target lesion length calcified OR 
> 50mm of calcium 	Eligible														
IVUS cannot cross lesion after one attempted pass	
 
Bilateral calcification AND $\geq \frac{1}{2}$ of target lesion length calcified OR 
Bilateral calcification AND >50mm of calcium 	Eligible														
$<180^\circ$ of calcification		Not Eligible														
All-cause death through 30-days of the clinical trial treatment, major amputation of the target limb, clinically-driven TLR.																
Amputation of the ankle joint and/or above.																
Failure of an investigational medical device to perform in accordance with its intended purpose when used in accordance with the instructions for use or CIP, or IB (per ISO 14155:2020)																

Term	Definition
Maximum balloon inflation pressure	Balloon inflation pressure used during pre-dilatation to achieve full balloon expansion with no visible waist.

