8.2 Secondary Endpoints

The following secondary endpoints will be evaluated:

1. Reduction in lesion stenosis both post-OAD and post-OAD+POBA [Angiographic Core Lab assessed] (absolute mean percentage change defined as the difference between the pre-procedure percent stenosis and the percent stenosis measured post-OAD and post-OAD+POBA)
2. Acute technical success defined per the PARC definition of achievement of a final residual stenosis <30% for stented and <50% for non-stented subjects by angiography at the end of the procedure [Angiographic Core Lab assessed] without severe angiographic complications defined as severe dissections (D-F), perforation, or distal emboli requiring additional treatment during the procedure [CEC adjudicated]
3. DCB Device Success defined as the ability to achieve successful delivery and deployment of all DCB to the target lesion as described per the Instructions for Use (IFU) within 3 minutes of insertion without removal and use of an additional device.
4. Target vessel patency at 6 months defined as absence of clinically-driven Target Lesion Revascularization (TLR) and ≤2.4 peak systolic velocity ratio (PSVR) as assessed by Duplex Ultrasound [Duplex Ultrasound Core Lab assessed]. Clinically-driven TLR is defined as repeat procedure performed for ≥50% stenosis confirmed by angiography within all or part of the target lesion after documentation of recurrent clinical symptoms of PAD following clinical trial treatment [CEC adjudicated]
5. Rate of severe angiographic complications defined as severe dissections (D-F), perforation, or distal emboli requiring additional treatment during the procedure [CEC adjudicated]
6. Acute procedure success defined as both acute technical success and absence of death, stroke, MI, acute onset of limb ischemia, index bypass graft or treated segment thrombosis, and/or need for urgent/emergent vascular surgery within 72 hours of the clinical trial treatment [CEC adjudicated]
7. Major Adverse Event (MAE) rate at 30 days and 6 months [CEC adjudicated] defined as:

- a) All-cause death through 30 days **or**
- b) Major amputation of the target limb **or**
- c) Clinically-driven TLR

8. Adverse Event rates at 30 days and 6 months [CEC adjudicated]
9. Distribution of Rutherford Classification compared to baseline at 30 days and 6 months
10. Change in Ankle Brachial Index (ABI) after clinical trial treatment compared to baseline

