## 6.4 Analysis Windows

Assessments will be made at baseline ( $\leq$  30 days prior to procedure), during the procedure, and post-procedure/discharge. Follow-up visits (analysis windows) are scheduled as office visits or phone call at the following time points post-procedure: 30-days (+14 days) and 6-months (+30 days). All windows will be calculated in days (i.e. 6-months will be calculated as 180 days).

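### The 6-month MAE rate counts deaths only to day 30 and censors later ones: label it so, treat late death as a competing event, and report mortality to day 210 beside it

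*SAP*

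**What the plan says.** The protocol lists as its seventh secondary endpoint "Major Adverse Event (MAE) rate at 30 days and 6 months [CEC adjudicated] defined as" a three-part composite. The death part is "All-cause death through 30 days"; major amputation of the target limb and clinically-driven TLR carry no day limit. The definitions table in Protocol 4 has the same structure: "All-cause death through 30-days of the clinical trial treatment, major amputation of the target limb, clinically-driven TLR".

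SAP 7.7.7 repeats the composite and analyses it on the mITT set and the FAS, "at the time-points of 30 days and 6 months as a time-to-event analysis". On timing it says "The 6-month rates will be evaluated at 210 days (180 days + 30-day visit window"), which fits the convention in SAP 6.4 that "All windows will be calculated in days (i.e. 6-months will be calculated as 180 days"). The rule for late deaths is in the first component: "death through 30-days (note: subjects with a death after 30-days will be considered censored on the date of death) or". On the components separately it says only that "The component rates of MAE may be presented".

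Protocol 25.4.3 attaches no formal test to any secondary endpoint.

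**The concern.** A rate called MAE at 6 months invites the reader to assume that it includes 6-month mortality. It does not. A subject who dies on day 60 leaves the risk set without an event, so the estimate can be the same in a study with no late deaths and in one with several.

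The censoring rule is also the wrong tool for what is left after day 30. Kaplan-Meier censoring treats the dead subject as someone who could still go on to amputation or TLR. Death rules both out, so the complement of the Kaplan-Meier curve overstates the probability of the composite as defined.

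No other planned 6-month summary in the readable text fills the gap. Target vessel patency (SAP 7.7.4) is restricted to subjects who attend the 6-month visit. Component rates are optional, and a death component taken from the MAE definition would stop at day 30 as well. At stake is how a secondary safety figure reads, in a study whose objective is safety and effectiveness data for commercialization in Japan.

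**Working it through.** **The plan's own figure.** 180 + 30 = 210 days, as SAP 7.7.7 states. The share of that span with no death component is (210 − 30)/210 = 180/210 = 85.7%. Against a nominal 180 days it is 150/180 = 83.3%. These are shares of time; they become shares of deaths only if the death hazard is constant.

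**Inputs for size.** The documents give no mortality, amputation or TLR rate, so the rates below are assumptions. N = 62 (SAP 3.5) is used only for scale. Hazards are constant within periods, and everyone is followed to day 210 unless an event occurs. That last point is a simplification, because Protocol 14.2 lets subjects exit at a visit from about day 180.

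Let h_N be the amputation/TLR hazard, with h_N = −ln(1 − q)/210 for a day-210 probability q, and let h_D be the death hazard.

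- Planned estimate (1 − KM, deaths counted to day 30, later deaths censored): 1 − exp(−30·h_D − 210·h_N)
- All deaths counted: 1 − exp(−210·(h_D + h_N))
- Cumulative incidence, death after day 30 competing: 1 − S + S·[h_N/(h_N + h_D)]·[1 − exp(−180·(h_N + h_D))], with S = exp(−30·(h_D + h_N))

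**Illustration A.** q = 10%, no deaths to day 30, mortality m in days 31-210. Here h_D is zero up to day 30 and −ln(1 − m)/180 after it, so the planned estimate is q and the all-death composite is 1 − 0.90 × (1 − m).

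| m | Late deaths in 62 | Planned | All deaths counted | Cumulative incidence |
|---|---|---|---|---|
| 2% | 1.2 | 10.0% | 11.8% | 9.92% |
| 3% | 1.9 | 10.0% | 12.7% | 9.87% |
| 5% | 3.1 | 10.0% | 14.5% | 9.79% |

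The planned estimate does not move as late mortality rises. Counting all deaths adds 1.8 to 4.5 points. The estimator change is 0.08 to 0.21 points.

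**Illustration B.** The death hazard is constant from day 0, so early deaths enter the planned figure as the SAP intends. For annual mortality a, h_D = −ln(1 − a)/365.

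| a | q | Planned | All deaths counted | Gap (points) | Cumulative incidence |
|---|---|---|---|---|---|
| 2% | 5% | 5.16% | 6.10% | 0.94 | 5.14% |
| 2% | 10% | 10.15% | 11.04% | 0.89 | 10.11% |
| 5% | 5% | 5.40% | 7.76% | 2.36 | 5.35% |
| 5% | 10% | 10.38% | 12.62% | 2.24 | 10.27% |
| 10% | 5% | 5.82% | 10.59% | 4.77 | 5.71% |
| 10% | 10% | 10.78% | 15.29% | 4.52 | 10.56% |

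Expected deaths in days 31-210 among 62 subjects are 0.6, 1.5 and 3.1 for the three mortality levels. The gap from omitted deaths runs from 0.9 to 4.8 points. The gap from the estimator runs from 0.02 to 0.21 points. One subject in 62 is 1.6 points.

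**The case against.** The strongest reply is that nothing here is an error. The 30-day limit on death is deliberate and the same in every place that defines MAE, and the SAP states the censoring rule openly. The endpoint is one of ten untested secondaries. All of that stands.

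It can also be said that late deaths are already reported. Protocol 16.4 requires deaths on the AE and Study Exit forms, and Protocol 18 lists death as an exit reason. SAP 7.1 tabulates exit reasons with percentages on the FAS. SAP 7.7.8 summarizes SAEs from day 31 to exit and lists each event with its timing and outcome. A reader might infer from the MAE rule that late deaths are hidden; these outputs show that they are not. What they lack is a mortality estimate to a fixed day with a confidence interval. The AE tables are organized by event term and split at day 30/31, so a fatal event may appear under its diagnosis.

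The competing-risk correction is numerically trivial here, and the planned estimator errs towards overstating harm. That is right. The case for changing it is correctness at no cost.

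Last, much of the SAP text on conventions and missing data (sections 6.2 and 6.3) is blacked out, so a further rule on mortality cannot be excluded.

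**Conclusion.** The point holds as an inexpensive improvement to a secondary safety estimate. The day-210 MAE rate cannot reflect deaths in days 31-210 and handles death by censoring where a competing-risk estimate is the right one. Omitting late deaths is the larger effect: about 2 to 4.5 points with 10% amputation/TLR and 2-5% late mortality, and 0.9 to 4.8 points over the wider grid. The estimator itself matters by at most about 0.2 points. All of these sizes rest on assumed rates and constant hazards. The primary endpoint, sample size and type I error are untouched.

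Two stronger readings are not supported. A reader might infer that the composite hazard must fall after day 30. Only the death contribution goes to zero; the total depends on the amputation/TLR hazard, for which the documents give no figure. In illustration B a rise in that hazard by a factor of 1.11 to 2.18, which is (h_N + h_D)/h_N, would offset the loss. A reader might also link the rule to the paclitaxel discussion in Protocol 26.2 and expect excess deaths by 6 months. That section places the reported signal at 2 and 5 years and says there was no difference at 1 year.

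**What to change.** Keep the protocol composite and amend SAP 7.7.7 as follows.

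1. Label the day-210 result '30-day death, or major amputation or clinically-driven TLR to day 210' wherever it is reported.
2. Replace censoring at death after day 30 with a cumulative-incidence (Aalen-Johansen) estimate in which death after day 30 is a competing event. Deaths to day 30 remain component events.
3. Beside it, report all-cause mortality to day 210 with a 95% CI. Show the numbers at risk, since subjects may exit from about day 180, and name an interval method that still works if there are no deaths.
4. Add a supportive version of the composite that counts all deaths to day 210.

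The data are already collected. The cost is SAP wording and a few extra table rows. The downside for the sponsor is a somewhat less favourable supportive 6-month figure.

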### **7.7.8 Adverse Event (AE) Rates**

Adverse event rates will be assessed on a subject level for the mITT and FAS. All site reported and CEC adjudicated reportable adverse events specified in the protocol will be included in the analysis. Adverse events

are collected starting at enrollment through subject exit from the study. Adjudicated AEs will be summarized by AE term and overall for number and percent of subjects experiencing each event, and number of events.

Adverse events summaries will be provided for the time-points of enrollment to 30 days, and 31 days to study exit in the following groups:

- Serious Adverse Event (SAE): Any AE that the CEC has determined meets the protocol definition of serious
- Adverse Device Effect (ADE): Any AE the CEC has determined meets the protocol definition of related to the use of the OAS
- Serious Adverse Device Effect (SADE): Any ADE that the CEC has the protocol definition of serious
- Unanticipated Serious Adverse Device Effect (USADE): Any SAE that the CEC has determined that by its nature, incidence, severity or outcome has not been identified in the current version of the risk analysis report

Any events for which the determination of seriousness and/or relatedness to the device cannot be determined by the CEC will count as serious and/or related for the purposes of this analysis.

In addition, a subject data listing of all reportable AEs will be presented from the time of enrollment to study completion and will include the following: adverse event term, AE onset date, days to event, seriousness, relationship to OAS and procedure, outcome, and date resolved (if applicable).

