Target lesion revascularization (TLR)	A repeat procedure occurring after the clinical trial treatment (percutaneous or surgical) that includes all or part of a target lesion treated during the clinical trial treatment.
Target vessel revascularization (TVR)	A repeat procedure occurring after the clinical trial treatment (percutaneous or surgical) that includes all or part of a target vessel treated during the clinical trial treatment.
Target vessel	
A target vessel is any vessel that contains the target lesion treated with the study device. The target vessel includes the target lesion as well as the entire length of native vessel upstream and downstream from the target lesion, including side branches.
 
For the arteries of the leg, the vasculature is divided into 3 vessel "levels:" aorto-iliac, femoral-popliteal, and tibial-crural.

Unanticipated Serious Adverse Device Effect (USADE)	
A serious adverse device effect which by its nature, incidence, severity or outcome has not been identified in the current risk assessment (per ISO14155:2020).
 
Note: Anticipated serious adverse device effect (ASADE) is an effect which by its nature, incidence, severity or outcome has been identified in the risk assessment.

Unstable Angina Pectoris	
 1. Ischemic discomfort (angina, or symptoms thought to be equivalent) ≥ 10 minutes in duration occurring 
 a) At rest, OR b) In an accelerating pattern with frequent episodes associated with progressively decreased exercise capacity.

Term	Definition
	
AND
 
2. At least one of the following:
 
 a) resting ECG evidence of acute myocardial ischemia; b) exercise or pharmacological stress testing evidence of inducible myocardial ischemia that is believed to be responsible for the ischemic symptoms/signs; c) angiographic evidence of new or worsening obstructive coronary artery disease and/or intracoronary thrombus that is believed to be responsible for the ischemic symptoms/signs; OR d) need for coronary revascularization of the presumed culprit lesion(s), as defined in c; 
AND
 
3. Negative cardiac biomarkers and no evidence of acute myocardial infarction (MI)

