16. ADVERSE EVENTS

16.1 Adverse Event Requirements

For the purposes of this study the following events will be collected:

- All Clinical Trial Treatment Adverse Events
- All SAEs
- All ADEs, SADEs, USADEs
 - For both the CSI Peripheral OAS and the Medtronic IN.PACT™ Admiral™ DCB

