16.2 Adverse Event Definitions

An **Adverse Event (AE)** is any disease or injury, or its clinical signs occurring in a subject who has been treated with an investigational device or post-marketing study device (Per Ordinance of the Ministry of Health and Welfare No.36)

A **Serious Adverse Events (SAE)** is an adverse event that (per ISO14155:2020):

- a) Led to death,
- b) Led to serious deterioration in the health of the subject, users, or other persons as defined by one or more of the following:
 - A life-threatening illness or injury, or
 - A permanent impairment of a body structure or a body function including chronic disease, or
 - In-patient or prolonged hospitalization, or
 - Medical or surgical intervention to prevent life-threatening illness or injury or permanent impairment to a body structure or a body function,
- c) Led to foetal distress, foetal death or a congenital abnormality or birth defect

Note: *Planned hospitalization for a pre-existing condition, or a procedure required by the CIP, without serious deterioration in health, is not considered a serious adverse event.*

An **Adverse Device Effect (ADE)** is an adverse event-related to the use of an investigational medical device (per ISO14155:2020).

Note 1: This definition includes adverse events resulting from insufficient or inadequate instructions for use, deployment, implantation, installation, or operation, or any malfunction of the investigational medical device.

Note 2: This definition includes any event resulting from use error or from intentional misuse of the investigational medical device.

Note 3: This includes 'comparator' if the comparator is a medical device.

A **Serious Adverse Device Effect (SADE)** is an adverse device effect that has resulted in any of the consequences characteristic of a serious adverse event (per ISO14155:2020).

An **Unanticipated Serious Adverse Device Effect (USADE)** is a serious adverse device effect which by its nature, incidence, severity or outcome has not been identified in the current risk assessment (per ISO14155:2020).

Note 1: Anticipated serious adverse device effect (ASADE) is an effect which by its nature, incidence, severity or outcome has been identified in the risk assessment.

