16.3 Adverse Event Relatedness

The relatedness of the AE will be classified by the Investigator for both the CSI Peripheral OAS and the Medtronic IN.PACT™ Admiral™ DCB and adjudicated by the CEC for the CSI Peripheral OAS. The Investigator will use the following definitions in classifying the relationship of the AE:

- **Peripheral Orbital Atherectomy System-Related:** AE is directly related to the investigational device(s) used in treatment of the lesion.
- **Clinical Trial Treatment Procedure-Related:** AE is directly attributable to the clinical trial treatment.
- **Target Limb-Related:** AE is related to the limb in which OA was performed.
- **IN.PACT Admiral Balloon-Related:** AE is directly related to the IN.PACT Admiral device used in treatment of the lesion

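### SAP 7.7.8 builds the USADE count from all SAEs and loses the device-relatedness condition that the protocol requires

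*SAP*

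**What the plan says.** SAP 7.7.8 sets out four groups for the adverse event summaries.

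- **SAE:** any adverse event that the CEC finds serious. Cause does not enter.
- **ADE:** any adverse event that the CEC finds related to use of the OAS.
- **SADE:** "Any ADE that the CEC has the protocol definition of serious". A verb is missing, but the line clearly starts from ADEs, so relatedness is carried in.
- **USADE:** the entry reads "Any SAE that the CEC has determined that by its nature, incidence, severity or outcome has not been identified", with the latest risk analysis report as the reference. This line starts from SAEs.

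A further rule in 7.7.8 says that events whose seriousness or relatedness the CEC cannot determine "will count as serious and/or related for the purposes of this analysis". The four groups are summarised for "enrollment to 30 days, and 31 days to study exit in the following groups".

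The protocol defines USADE twice in the same terms. Section 4 has "A serious adverse device effect which by its nature, incidence, severity or outcome has not been identified in the current risk assessment"; section 16.2 says that a USADE "is a serious adverse device effect which by its nature, incidence, severity or outcome has not been identified in the current risk assessment". In both sections a SADE is an ADE with a serious consequence, and an ADE is an adverse event related to use of the investigational device.

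**The concern.** The SAP keeps the name of the category but changes what goes into it. Under the protocol, a USADE must be serious, device-related and unanticipated. Under the SAP line it need only be serious and unanticipated. If the line is programmed as it stands, the table will present as unanticipated device effects some events that the CEC has judged to have nothing to do with the device.

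Such events will be in the data. Protocol 16.1 ("For the purposes of this study the following events will be collected") lists all SAEs, whatever their cause. A document of device risks is also not where one would expect to find unrelated illnesses. That last step is an inference, because the risk report is not among the documents.

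The study's stated objective is to collect safety and effectiveness data to support commercialisation in Japan, so its table of unanticipated serious device effects should mean what the protocol says it means.

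A second, narrower matter is the time windows. Secondary endpoint 8 (protocol 8.2) asks for adverse event rates at 30 days and at 6 months. The first window gives the 30-day rate for the four groups. No 6-month rate is stated for them.

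**Working it through.** **USADE definition.** No published figure bears on this, so the check is a comparison of the definitions. Let S = serious, R = related to the OAS, and U = not identified in the risk document.

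| Category | Protocol 4 and 16.2 | SAP 7.7.8 |
|---|---|---|
| SADE | S and R | S and R |
| USADE | S and R and U | S and U |

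There are 2 × 2 × 2 = 8 combinations. The four with S = 0 are not USADEs under either document. The four with S = 1 are:

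| S | R | U | USADE, protocol | USADE, SAP | SADE, SAP |
|---|---|---|---|---|---|
| 1 | 1 | 1 | yes | yes | yes |
| 1 | 1 | 0 | no | no | yes |
| 1 | 0 | 1 | **no** | **yes** | no |
| 1 | 0 | 0 | no | no | no |

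The definitions differ in exactly one combination: serious, unrelated, unanticipated. Three things follow.

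1. Under the SAP, USADE is not a subset of SADE, so the USADE count can exceed the SADE count. Under the protocol that is impossible.
2. The error runs one way: it can only raise the USADE count.
3. The undetermined-events rule does not repair it. The rule covers only events that the CEC cannot classify, not those it has judged unrelated. Its relatedness part also has no effect on the USADE row, because relatedness is not an input to that row.

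The missing condition can be applied with data already planned: under protocol 16.3 relatedness is "adjudicated by the CEC for the CSI Peripheral OAS".

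**Size.** The affected count lies between 0 and the number of SAEs that the CEC judges unrelated to the OAS. On an mITT set of 62 (SAP 3.5), each misclassified subject adds 1/62 = 0.0161, or 1.6 percentage points. On a larger mITT set or FAS it adds less.

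**Windows.** Let p1 be the proportion of subjects with an event from enrolment to 30 days, and p2 the proportion from day 31 to exit. A subject may have events in both, so for the cumulative proportion p:

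max(p1, p2) ≤ p ≤ min(1, p1 + p2)

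When p1 + p2 ≤ 1, the width is p1 + p2 − max(p1, p2) = min(p1, p2). For illustration, with p1 = p2 = 10%, p lies anywhere from 10% to 20%. Numbers of events do add across the windows; percentages of subjects do not.

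**The case against.** The strongest reply is that this is a slip of SAE for SADE. The line keeps the words device effect in its label, the SADE line above it is also garbled, and SAP section 1 asks to be read together with the protocol, which is unambiguous. A sensible programmer would follow the protocol. Even if the line were taken literally, it could only over-count and could not hide a true USADE. The subject listing shows relationship to the OAS, regulatory reporting runs through sponsor review under protocol 16.4, and secondary endpoints carry no hypothesis test.

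Most of this stands as a limit on the consequence. A slip is the likely cause, and the effect is confined to a descriptive table. It does not remove the error. The line is an operative definition in a SAP whose programming may go to an external vendor (SAP 4.4). SAP section 8 requires deviations from the SAP to be reported, so quietly programming the protocol version would itself be a deviation. Over-counting is not harmless either, since it sets aside the CEC's own adjudication and could bury a genuine signal among unrelated events.

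On the windows, it is fair to say that endpoint 8 does not name the four groups, and that an untimed summary covers adjudicated events by term and overall. Cumulative subject counts for SAE, ADE and SADE could also be rebuilt from the listing, which gives days to event, seriousness and relatedness. But the listing's stated contents do not include whether an event was anticipated, and a reader should not have to rebuild a rate from a listing. It is also true that SAP 6.4 counts 6 months as 180 days and that some subjects may exit after day 210; the fix below deals with both.

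**Conclusion.** The concern holds. The USADE line in SAP 7.7.8 contradicts both protocol definitions and breaks the nesting of USADE within SADE in the SAP's own scheme. The textual mismatch is certain. Its effect on the results is not known: it depends on how many serious events the CEC judges unrelated and on what the risk analysis report lists, and neither is in the documents. The figure of 1.6 percentage points is the effect of one misclassified subject on 62, not an estimate of the total, and it assumes that the line is programmed literally. The primary endpoint, its test and the sample size are untouched.

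The window point is correct but minor. For the four groups, the 6-month subject-level rate is left undetermined by up to the smaller of the two window rates. The case for amending the SAP rests on the USADE line alone.

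**What to change.** In SAP 7.7.8:

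1. Start the USADE line from SADE instead of SAE and leave the rest of the line unchanged. USADE then means serious, related and unanticipated, as in protocol 4 and 16.2, and the rule for undetermined events reaches it through SADE.
2. In the same edit, supply the missing verb in the SADE line, since the USADE line will now depend on it.
3. For the SAE, ADE, SADE and USADE groups, add a cumulative column from enrolment to 6 months, with number and percentage of subjects and number of events. Use the cut-off that SAP 7.7.7 already applies to 6-month rates, 180 + 30 = 210 days, and say so explicitly because SAP 6.4 counts 6 months as 180 days. Events after day 210 remain in the existing window to study exit.

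The cost is one word for the definition, one verb, and one extra column in four summaries. No new data are needed.
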